5. STUDY DRUG INFORMATION

Instructions for the receipt, inspection, storage, preparation, administration, and disposal of KZR-616 are to be provided in a separate Pharmacy Manual at each clinical site.

5.1. Physical Description of the Study Drugs

KZR-616 Lyophile, 125 mg/vial, is supplied as a refrigerated lyophilized drug product containing 125 mg of KZR-616 (150 mg of KZR-616 maleate) and [REDACTED] (inactive excipient) in single use 3.0-mL borosilicate glass vial. Each vial is reconstituted with sterile water for injection (WFI) prior to administration.

Placebo will be sterile WFI and will be supplied by the individual clinical sites.

5.2. Packaging and Labeling

The lyophilized drug product will be supplied in 3-mL single-use vials packaged in multivial cartons.

The Sponsor or its representatives will be responsible for labeling according to local regulatory requirements.

All packaging and labeling operations will be performed according to Good Manufacturing Practice (GMP) for Medicinal Products and the relevant regulatory requirements.

5.3. Supply, Dispensing, Storage, and Investigational Product Accountability

The Sponsor or its representatives will supply KZR-616 Lyophile to the investigational site. The study drug supplies provided for this study will be manufactured under current GMP, will be subject to release, and will be suitable for human use.

Only participants enrolled in the study may receive study drug and only authorized staff may supply or administer study drug.

KZR-616 Lyophile must be stored in a refrigerator at 2°C to 8°C. Reconstituted study drug can be stored until use in a refrigerator (recommended) controlled at 2°C to 8°C for a maximum of 24 hours or at room temperature at 15°C to 30°C for a maximum of 4 hours, or until use, whichever occurs first. All study drug should be stored in an environmentally controlled and monitored (manual or automated) area in accordance with the labeled storage conditions. Access to study drug must be limited to the Investigator and authorized study personnel.

Further information of the storage, preparation, and administration of study drug will be provided in a Pharmacy Manual.

On receipt of the study drug, the Investigator (or designee) will conduct an inventory of the supplies and verify that study drug supplies are received intact and in the correct amounts.

The study monitor may check the study supplies at each study center at any time during the study.

The Investigator, institution, or the head of the medical institution (where applicable) is responsible for study treatment accountability, reconciliation, and record maintenance (such as receipt, reconciliation and final disposition records).

It is the responsibility of the study monitor to ensure that the Investigator (or designee) has correctly documented the amount of the study drug received, dispensed, and returned on the dispensing log that will be provided. A full drug accountability log will be maintained at the study center at all times. The study monitor will perform an inventory of study drug at the closeout visit to the study center. All discrepancies must be accounted for and documented.

6. DOSAGE AND STUDY DRUG ADMINISTRATION

6.1. Study Drug Administration

KZR-616 and matching placebo will be administered by SC injection once weekly according to the randomized treatment schedule shown in [Table 1](#). Patients should be monitored for 2 hours after dosing at W0 and W16.

Further details regarding drug product formulation, preparation, and administration of KZR-616 will be provided in a separate Pharmacy Manual.

Table 1 **Study Drug Administration**

Treatment Arm	Study Drug Administered	
	Treatment Period 1 ^a	Treatment Period 2 ^a
	Week 0 to Week 16 ^b	Week 16 to Week 32 ^b
Arm A	KZR-616 W0 and W1: 30 mg W2-W15: 45 mg	Placebo
Arm B	Placebo	KZR-616 W16 and W17: 30 mg W18-W31: 45 mg

a Treatment Period 1 is from the time of dosing on Day 1 of Week 0 and continues until immediately before dosing at Week 16 (approximately Day 113). Treatment Period 2 begins with administration of the first dose at Week 16 and continues through Week 32.

b Study drug will be administered via subcutaneous injection once weekly. Patients need to be monitored for 2 hours after dosing at Week 0 and at Week 16. The last dose of study drug is at W15 for Treatment Period 1 and at W31 for Treatment Period 2.

6.1.1. Dosing Criteria

All patients must meet the following criteria before each dose:

- Absolute neutrophil count $\geq 1.0 \times 10^9/L$ as of the most recent laboratory testing
- Hemoglobin $\geq 8.0 \text{ g/dL}$ and $\leq 16.5 \text{ g/dL}$ as of the most recent laboratory testing
- Platelets $\geq 50,000/\text{mm}^3$ and $\leq 1,000,000/\text{mm}^3$ as of the most recent laboratory testing
- Serum ALT or AST $\leq 3 \times \text{ULN}$ and total bilirubin $< 2 \times \text{ULN}$
- Non-ISR AEs \leq Grade 2.

Dosing should be held until the AE improves to \leq Grade 2 or the laboratory abnormality is within the range to allow dosing (please see [Section 6.1.4.2](#) regarding missed doses), unless there is Medical Monitor or Sponsor approval to permit dosing. Any laboratories with values that preclude dosing should be repeated as soon as possible (as per [Section 7.2.6.10](#)).

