10. History of any concurrent illness (eg, asthma) that has required treatment with oral or parenteral corticosteroids for more than a total of 2 weeks within the last 24 weeks prior to Screening
11. Any of the following laboratory values at Screening:
 - a. Estimated glomerular filtration rate <45 mL/min by CKD-EPI (Chronic Kidney Disease Epidemiology Collaboration) equation
 - b. Hemoglobin <10 g/dL
 - c. White blood cell (WBC) count <3.0 × 10⁹/L
 - d. Absolute neutrophil count (ANC) <1.5 × 10⁹/L (1500/mm³)
 - e. Platelet count <100 × 10⁹/L
 - f. Serum AST or serum ALT >2.5 × ULN (unless considered consistent with muscle origin)
 - g. Serum alkaline phosphatase >2.5 × ULN
 - h. Total bilirubin >1.5 × ULN (3 × ULN for patients with documented Gilbert's syndrome)
 - i. Thyroid stimulating hormone outside of the central laboratory normal range
 - j. IgG <500 mg/dL.
12. Presence of New York Heart Association Class III or IV heart failure, or uncontrolled blood pressure (systolic blood pressure ≥160 mm Hg or diastolic blood pressure ≥100 mm Hg at rest), or QT interval with Fredericia's correction (QTcF) or Bazett's correction (QTcB) >480 msec on ECG
13. Major surgery within 12 weeks before Screening, major surgery planned during the study period, or any surgery planned during the study period that would require an alteration of concomitant immunosuppressant or corticosteroid therapy or additional corticosteroid therapy
14. Clinical evidence of significant unstable or uncontrolled diseases (eg, cardiac [including congestive heart failure, hypertension, angina, or recent {<6 months prior to Screening} myocardial infarction], pulmonary [including chronic obstructive pulmonary disease, asthma requiring systemic corticosteroid therapy, pulmonary hypertension, or interstitial lung disease], hematologic, gastrointestinal, endocrinologic [eg, hypothyroidism, diabetes], hepatic, renal, neurological, or infectious) that, in the opinion of the Investigator or Sponsor, could confound the results of the study, put the patient at undue risk, or interfere with protocol adherence
15. Evidence of current or previous clinically significant disease, medical condition (including abnormal laboratory values), or finding in the medical examination that in the Investigator's or Sponsor's opinion would compromise the safety of the patient or the ability to interpret the data

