Table 3 Schedule of Assessments for the Study Drug Administration Visits during Treatment Period 1

Study Period	Treatment Period 1											
	3	4	5	7	8	9	11	12	13	15	16	17
Visit No.	3	4	5	7	8	9	11	12	13	15	16	17
Start of Week	1	2	3	5	6	7	9	10	11	13	14	15
Day	8±1	15±1	22±1	36±1	43±1	50±1	64±1	71±1	78±1	92±1	99±1	106±1
Vital signs ^a	X	X	X	X	X	X	X	X	X	X	X	X
Study drug administration	X ^b	X	X	X	X	X	X	X	X	X	X	X

Note: Home health service will be arranged for patients who choose not to return to investigative site for study drug administration weekly.

- a. Vital signs will be collected before dosing. Blood pressure and pulse rate should be collected after the patient has had at least 5 minutes of rest in the seated position. It is recommended that blood pressure is measured using the same arm at each assessment.
- b. Patients need to be monitored for 2 hours after dosing at Visit 3.

Table 4 Schedule of Assessments for Treatment Period 2 and Safety Follow-up

Study Period	Treatment Period 2				SFU		
	18	22	26	30	34/ETV ^a	35	36/EOS
Visit No. and or Name	16	20	24	28	32	36	40
Start of Week							
Day	113±1	141±1	169±1	197±1	225±2	253±3	281±3
PK and PD assessments	Predose	Postdose					
Concomitant therapy							
Pregnancy test ^b	X		X	X	X		
Physical examination ^c	X			X	X		X
Vital signs and weight ^d	X		X	X	X	X	X
12-lead ECG ^e	X		X				X
MMT-8 ^f	X		X	X	X	X	X
MDAAT, MDGA, MDGIC ^f	X		X	X	X	X	X
FI-2 (dominant side only) ^f	X						X
FI-3 ^f	X			X			X
Sit-to-stand test ^f			X		X		X
MDI ^f	X					X	
CDASI ^g	X		X	X	X	X	X
PtGADA, HAQ-DI, PGIC ^h	X		X	X	X	X	X
PROMIS-29, EQ-5D-5L ^h	X		X				X
HRU ^h	X			X		X	X
PtGADD ^h	X					X	X
TSQM ^h	X		X			X	X
Peak Pruritus NRS ^{g,h}	X		X	X	X	X	X
Hematology, chemistry ⁱ , CRP, and aldolase	X		X	X	X	X	X
Erythrocyte sedimentation rate ^j	X		X	X	X	X	X
Urinalysis ^k	X		X	X	X	X	X
Quantitative immunoglobulins ^l	X					X	
Autoantibodies ^m	X					X	
PK assessment ⁿ	X	X					
PD assessment ^o	X	X				X	
Cytokines/proteomics and leukocyte subsets ^p	X		X			X	
Gene expression and DNA methylation profiling (RNA) ^q	X		X			X	
Skin and/or muscle biopsies ^r	X					X	
Study drug administration ^s	X ^s		X	X	X		
Adverse events							

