7.2.6.10. Clinical Laboratory Tests

Clinical laboratory tests for safety (hematology, serum chemistries, urinalyses, coagulation tests, serum pregnancy) and other tests during scheduled visits will be performed at a central laboratory. Urine pregnancy tests and erythrocyte sedimentation rate (ESR) will be performed locally using an approved test; TB testing may be performed locally or centrally using a licensed test.

Clinical laboratory results the Investigator deems clinically significantly abnormal should be repeated ideally within 48 to 72 hours from when the result became available. Guidance for laboratory values that could be considered clinically significantly abnormal is provided in [Appendix B](#). Certain clinically significantly abnormal laboratory values may also influence continued dosing as per [Section 6.1.1](#).

Unscheduled or additional laboratory samples may be collected and analyzed by local laboratories if immediate results are necessary for management of TEAEs or dosing determination. Unless otherwise noted, when scheduled simultaneously with a dosing visit, samples for laboratory evaluations should be collected prior to administration of the study drug.

Detailed instructions for sample collection, processing, storage and shipment will be provided in the Laboratory Manual.

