8.1.2. Individual Patient Stopping Rules

If any of the following events occur in an individual patient, administration of study drug to the patient should be interrupted until a review of the accumulated safety data is undertaken by the DMC.

- Any event that fulfills criteria for a Study Stopping Rule (per [Section 8.1.1](#)), unless due to obvious alternative etiology
- Any event that, in the opinion of the Investigator, Medical Monitor, DMC, or Sponsor, contraindicates further dosing

After such a review, the DMC may recommend the patient resume dosing, including consideration for any prophylactic interventions (eg, as per [Section 6.1.3](#)); reduce their dose (as per [Section 6.1.4.1](#)), or discontinue dosing.

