Appendix B: Potentially Clinically Significantly Abnormal Laboratory Values

Laboratory Parameter	Abnormal Value
Hematology	
Absolute neutrophil count	$<1.0 \times 10^9/\text{L}$
Hemoglobin	$<8.0 \text{ g/dL}$ or $>16.5 \text{ g/dL}$
Leukocytes (total white blood cell)	$<1.5 \times 10^9/\text{L}$
Platelets	$<50,000/\text{mm}^3$ or $>1,000,000/\text{mm}^3$
Clinical Chemistry	
Bicarbonate (CO_2)	$\leq 10 \text{ mEq/dL}$
Magnesium	$<0.9 \text{ mg/dL}$ or $>3.0 \text{ mg/dL}$
Potassium	$<3.0 \text{ mmol/L}$ or $>6.0 \text{ mmol/L}$
Sodium	$<130 \text{ mmol/L}$ or $>155 \text{ mmol/L}$
Liver Function Tests	
Alanine aminotransferase	$>3 \times \text{ULN}$ (unless due to muscle origin)
Alkaline phosphatase	$>5 \times \text{ULN}$
Aspartate aminotransferase	$>3 \times \text{ULN}$ (unless due to muscle origin)
Total bilirubin	$>2 \times \text{ULN}$
Renal Function Tests	
Creatinine	$>3.0 \text{ mg/dL}$
Other Chemistry	
Albumin	$<2 \text{ g/dL}$
Calcium	$<7.0 \text{ mg/dL}$ or $>12.5 \text{ mg/dL}$
Glucose	$<40 \text{ mg/dL}$ or $>250 \text{ mg/dL}$

Abbreviations: dL=deciliter; L=liter; mg=milligram; mm^3 =cubic millimeter; mmol=millimole; ULN=upper limit of the laboratory reference (normal) range.

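### The pre-dose enzyme criterion in Section 6.1.1 joins ALT and AST with *or*, so a patient with one of them above 3 × ULN still meets it

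*Combined protocol and SAP*

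**What the plan says.** Section 6.1.1 (Dosing Criteria) gives a list, all of which must be satisfied before every dose. It covers neutrophils, hemoglobin, platelets, liver tests and the grade of non-injection-site adverse events. The liver line asks for "Serum ALT or AST" no higher than 3 × ULN and total bilirubin below 2 × ULN. A patient who fails a criterion is held "unless there is Medical Monitor or Sponsor approval to permit dosing". The section adds: "Any laboratories with values that preclude dosing should be repeated as soon as possible".

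Three other places bear on the same enzymes:

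- Exclusion 11f in Section 4.3 excludes a patient if either AST or ALT is above 2.5 × ULN, "unless considered consistent with muscle origin".
- Appendix B lists ALT and AST on separate rows, each flagged above 3 × ULN "unless due to muscle origin".
- Section 7.2.6.10 describes Appendix B as "Guidance for laboratory values that could be considered clinically significantly abnormal", and refers any effect of such values on dosing back to Section 6.1.1.

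Tables 2 and 4 schedule chemistry every four weeks. At the weekly dosing visits in between, Tables 3 and 5 list only vital signs and the injection; on the former their footnote says: "Vital signs will be collected before dosing".

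**The concern.** In a rule that stops something, such as exclusion 11f, *or* is the cautious word: either raised enzyme is enough to exclude. In a rule that permits something, *or* does the opposite: either normal enzyme is enough to dose. Section 6.1.1 is a permitting rule and keeps *or* for the two transaminases.

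On the literal reading, a patient with one enzyme above 3 × ULN and bilirubin below 2 × ULN meets the line. None of the three steps in Section 6.1.1 then follows: no hold, no approval by the Medical Monitor or Sponsor, and no repeat test, since the repeat applies only to values that preclude dosing.

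Where the rise comes from muscle, dosing agrees with the exceptions in Appendix B and exclusion 11f. The conflict is therefore confined to single-enzyme rises not attributed to muscle. What is at stake is patient safety under a rule checked before every injection, and consistent use of that rule across up to about 18 sites.

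**Working it through.** There is no power or sample-size figure to reproduce. The check is one of logic, followed by a count of how many doses each laboratory draw stands behind.

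**1. The line as written against each enzyme complying.** Take bilirubin below 2 × ULN and rises not attributed to muscle.

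- Literal rule: (ALT ≤ 3 *or* AST ≤ 3) and bilirubin < 2.
- Each-enzyme rule: ALT ≤ 3 and AST ≤ 3 and bilirubin < 2.

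| ALT vs 3 × ULN | AST vs 3 × ULN | Literal | Each enzyme |
|---|---|---|---|
| within | within | pass | pass |
| above | within | pass | hold |
| within | above | pass | hold |
| above | above | hold | hold |

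The readings differ in 2 of 4 cases, those with exactly one enzyme above the limit. A grid of ALT and AST at 2, 4 and 10 × ULN and bilirubin at 1 and 2.5 × ULN (3 × 3 × 2 = 18 combinations) gives the same picture. The 4 that differ are ALT/AST of 2/4, 2/10, 4/2 and 10/2, all with bilirubin at 1 × ULN. The literal rule has no upper bound on the raised enzyme: ALT 10 × ULN with AST 2 × ULN passes.

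**2. How the neighbouring limits were turned from flags into permissions.**

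| Parameter | Appendix B (flag) | Section 6.1.1 (permit) |
|---|---|---|
| Hemoglobin, g/dL | < 8.0 *or* > 16.5 | ≥ 8.0 *and* ≤ 16.5 |
| Platelets, per mm³ | < 50,000 *or* > 1,000,000 | ≥ 50,000 *and* ≤ 1,000,000 |
| ALT, AST | each > 3 × ULN, on its own row | ALT *or* AST ≤ 3 × ULN |

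For hemoglobin and platelets the connector changes along with the inequality. For the transaminases the inequality is permissive but the connector stays *or*. This points to a slip, although the documents do not describe how the line was drafted.

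**3. Doses behind each draw.** Chemistry visits during dosing are W0, 4, 8, 12, 16, 20, 24 and 28, which is 8 per patient.

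- Draws: 24 × 8 = 192.
- Doses: 24 × 32 = 768, of which 24 × 16 = 384 are KZR-616.
- Doses per draw: 768 / 192 = 4.

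This assumes that the latest available result governs. Section 6.1.1 says so for the blood counts but not for the liver tests. Because scheduled chemistry goes to a central laboratory, a result may govern the four doses after the visit rather than those starting at it; the ratio is the same.

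**The case against.** The strongest reply is that the intended meaning is clear enough. The blood-count and liver limits in Section 6.1.1 are those of Appendix B restated as permissions, apart from bilirubin at exactly 2 × ULN. Appendix B treats the enzymes separately, and Section 7.2.6.10 ties abnormal values to Section 6.1.1. The holding sentence in 6.1.1 speaks of a single laboratory abnormality returning to range, which fits a test of each value. Many sites would read the line as meant.

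Harm would also need several things together: exactly one enzyme raised, a cause other than muscle, bilirubin below its limit, no non-injection-site event above Grade 2, a site reading the line literally, and an Investigator who does not regard as significant a value that Appendix B names. If the Investigator does, Section 7.2.6.10 asks for a repeat, ideally within 48 to 72 hours. Section 8.1.2 allows interruption for "Any event that, in the opinion of the Investigator, Medical Monitor, DMC, or Sponsor, contraindicates further dosing". Transaminase changes that form part of a systemic injection reaction are events of special interest, reportable within 24 hours.

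Much of this stands, and it limits how often harm could follow. It does not mend the rule. Section 7.2.6.10 sends the reader back to the defective line and sets no hold of its own. The Grade 2 criterion works only if the value is recorded and graded as an adverse event. Section 8.1.2 and the repeat test need someone's judgment, and reporting an event of special interest does not itself stop a dose. A fixed pre-dose criterion is there so that the hold does not rest on such judgments.

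Nor can every site be relied on to apply the stricter reading. It would hold each dose, short of approval, in a patient admitted under the muscle-origin exception whose enzymes stay above 3 × ULN. That gives a site a practical reason to use the literal wording, though this is inference.

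**Conclusion.** The concern holds. As written, the enzyme criterion fails only when both ALT and AST exceed 3 × ULN, and no other text requires each to comply. The error lets through 2 of the 4 within/above combinations, and one scheduled draw stands behind 4 weekly doses.

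The 2-of-4 count describes the rule and is not a frequency. The number of affected doses cannot be estimated, because the documents give no rate of single-enzyme rises not due to muscle. The conclusion rests on the literal wording. It does not claim that such a patient would certainly be dosed, since partial safeguards remain and the intent is very probably that neither enzyme exceed the limit.

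This is a defect in an operative safety rule and should be corrected. It has no bearing on the primary analysis or the sample size.

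**What to change.** Reword the line in Section 6.1.1 to:

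*ALT and AST each ≤ 3 × ULN (unless due to muscle origin) and total bilirubin < 2 × ULN.*

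The muscle-origin exception needs to go in with the same edit. Replacing *or* by *and* alone would hold doses in patients whom exclusion 11f deliberately admits, and held doses count towards the missed-dose limits in Section 6.1.4.2 (2 consecutive, 4 in total). With the exception, a patient whose two enzymes are both raised from muscle would no longer need approval for each dose, in line with Appendix B. The entry limit of 2.5 × ULN and the dosing limit of 3 × ULN need not be made equal, and the existing override by the Medical Monitor or Sponsor can stay.

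The cost is one line in the next amendment, with no added scheduled procedure. There may be some extra held doses, repeat tests or calls to the Medical Monitor for single-enzyme rises not due to muscle.

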6.1.2. Administrative Site

A different SC injection site should be used for each administration. Injection sites should be rotated (eg, 4 abdominal quadrants, posterior upper arms, anterior thighs), and a minimum of 4 weeks should separate injections to the same site.

6.1.3. Monitoring of Dose Administration

Systemic injection reactions have been observed with KZR-616 and other proteasome inhibitors; the following guidance is based on these known experiences^{45,23} and may be modified as clinical experience with KZR-616 evolves and matures.

In KZR-616-001, 4 of 12 healthy volunteer subjects who received 60 mg KZR-616 SC experienced AEs with the preferred term of adverse drug reaction; consisting of hypotension, tachycardia, nausea, vomiting, rigors, and/or chills, associated with an acute phase-like response, including leukocytosis and elevated C-reactive protein (CRP), which occurred approximately 8 to 12 hours after dosing. These events are similar to the infusion-related reactions observed with the currently marketed proteasome inhibitor carfilzomib, which generally occur in the first cycle of dosing.

Systemic injection reactions with other proteasome inhibitors include a number of signs and symptoms, including fever, chills, myalgia, facial swelling or flushing, vomiting, weakness, hypotension, chest tightness, and shortness of breath, as well as abnormalities in laboratory values (eg, creatinine, transaminases). However, the relative roles of the immunoproteasome versus constitutive proteasomes to these specific events are not known. The individual signs/symptoms of systemic injection reactions must be reported as AESIs within 24 hours using the AE electronic case report form (eCRF) (refer to [Section 9.5.1](#)).

With other proteasome inhibitors, prophylactic measures such as pre-dose hydration and low-dose dexamethasone (4 mg) reduce the incidence and severity of infusion-related reactions. Therefore, upon the development of signs and/or symptoms suggestive of a systemic drug reaction, the following interventions are suggested:

- Supportive measures, including the administration of oral and/or IV fluids, antiemetics, acetaminophen, antihistamines and/or systemic corticosteroids (eg, prednisone 25 mg – equivalent to 4 mg of dexamethasone)
- Collection of serum and/or plasma samples for analysis of potentially elevated levels of eg, cytokines, histamines
- For patients who develop signs and/or symptoms that may be consistent with a cardiac etiology (eg, hypo- or hypertension, tachycardia, arrhythmia, or abnormal cardiac enzymes), the following should be obtained to rule out cardiac toxicity which has been described with proteasome inhibitors:
 - Serial ECGs, cardiac enzymes (eg, CK-MB, troponins, B-type natriuretic peptide [BNP]) to rule out myocardial infarction
 - Echocardiogram, unless heart failure can otherwise be ruled out by the preceding investigations.

- Prophylactic measures may be considered at the time of the first dose, or with subsequent doses if signs and/or symptoms consistent with a systemic drug reaction develop, including:
 - Fluid hydration, eg, 30 mL/kg orally at least 48 hours prior to dosing; and/or 250 to 500 mL IV after dosing if symptoms are present
 - Antiemetics, acetaminophen, and antihistamines
 - Systemic corticosteroids (eg, dexamethasone 4 mg or prednisone 25 mg) prior to subsequent doses. Use of systemic corticosteroids for prophylaxis should be discussed in advance with the Medical Monitor as their use could confound efficacy assessments.

